#### 12.2.2. Relationship to Study Drug

One of the following categories in Table 6 should be selected based on medical judgment, considering the definitions below and all contributing factors.

Related	A clinical event, including laboratory test abnormality, occurs in a plausible time relationship to treatment administration, and which cannot be explained by concurrent disease or other medications or chemicals. The response to withdrawal of the treatment (dechallenge a ) should be clinically plausible. The event must be definitive pharmacologically or phenomenologically, using a satisfactory rechallenge b procedure if necessary.
Probably related	A clinical event, including laboratory test abnormality, occurs within a reasonable time sequence to administration of the treatment, unlikely to be attributed to concurrent disease or other medications or chemicals, and which follows a clinically reasonable response on withdrawal (dechallenge). Rechallenge information is not required to fulfill this definition.
Possibly related	A clinical event, including laboratory test abnormality, occurs within a reasonable time sequence to administration of the treatment, but which could also be explained by concurrent disease or other medications or chemicals. Information on treatment withdrawal may be lacking or unclear.
Unlikely to be related	A clinical event, including laboratory test abnormality, occurs with a temporal relationship to treatment administration that makes a causal relationship improbable, and in which other medications, chemicals, or underlying disease provide plausible explanations.
Unrelated	A clinical event, including laboratory test abnormality, occurs with little or no temporal relationship with treatment administration. May have negative dechallenge and rechallenge information. Typically explained by extraneous factors (e.g., concomitant disease, environmental factors, or other medications or chemicals).

Table 6:Adverse Event Causality Definition

a Dechallenge is when a medication suspected of causing an AE is discontinued. If the symptoms of the AE disappear partially or completely, within a reasonable time from medication discontinuation, this is termed a positive dechallenge. If the symptoms continue despite withdrawal of the medication, this is termed a negative dechallenge. Note that there are exceptions when an AE does not disappear upon discontinuation of the medication, yet medication-relatedness clearly exists (e.g., as in bone marrow suppression, fixed medication eruptions, or tardive dyskinesia)

b Rechallenge is when a medication suspected of causing an AE in a specific subject in the past is readministered to that subject. If the AE recurs upon exposure, this is termed a positive rechallenge. If the AE does not recur, this is termed a negative rechallenge.

## 12.3. Recording Adverse Events

Adverse events should be collected and recorded for each subject from the date that the first study dose was taken until the end of their participation in the study (i.e., the subject has discontinued or completed the study). Only those AEs that occurred while on study drug that have not been resolved will be followed until resolution or stabilization.

Following the end of the subject's participation in the study, the PI or an authorized delegate should report SAEs "spontaneously" if considered at least possibly related to study medication.

Adverse events may be volunteered spontaneously by the study subject, or discovered by the study staff during physical examinations or by asking an open, non-leading question such as, "How have you been feeling since you were last asked?" All AEs and any required remedial action will be recorded in the subject's source documentation and transcribed onto the appropriate CRF page for the study period indicated. The nature of AE, date (and time, if known) of AE onset, date (and time, if known) of AE outcome to date, severity, and action taken of the AE will be documented together with the PI or an authorized physician's assessment of the seriousness of the AE and causal relationship to study medication and/or study procedure (at the time of assessment).

All AEs should be recorded individually in the study subject's own words (verbatim) unless, in the opinion of the PI or an authorized physician, the AEs constitute components of a recognized condition, disease, or syndrome. In the latter case, the condition, disease, or syndrome should be named rather than each individual symptom. The AEs will subsequently be coded using the MedDRA.

## 12.4. Treatment and Follow-Up of AEs

Appropriate measures should be taken to treat AEs as necessary, and the response of the study subject should be monitored and recorded. Clinical, laboratory, and diagnostic measures should be obtained as needed, and the results of which should be recorded in the subject's source documentation and transcribed onto the appropriate CRF page.

All SAEs will be followed until resolution, stabilization of the condition, the event is otherwise explained, or the subject is lost to follow-up.

## 12.5. Serious Adverse Events (SAEs)

An AE is considered serious if it meets one or more of the following criteria:

- Results in death
- Is life-threatening (i.e., a subject is at immediate risk of death at the time of the event, not an event where occurrence in a more severe form might have caused death)
- Requires inpatient hospitalization or prolongation of existing hospitalization
- Results in persistent or significant disability/incapacity
- Results in a congenital anomaly/birth defect
- Is another important medical event (see below).

Important medical events that do not result in death, are not life-threatening, or do not require hospitalization may be considered SAEs when, based on appropriate medical judgment, they may jeopardize the subject and may require medical or surgical intervention to prevent one of the outcomes listed above. Examples of such medical events include allergic bronchospasm requiring intensive treatment in an emergency room or in a physician's office, blood dyscrasias or seizures that do not result in inpatient hospitalization, and the development of drug dependency or drug abuse. A distinction should be drawn between serious and severe AEs.

Severity is a measure of intensity whereas seriousness is defined by the criteria above. For example, a mild degree of gastrointestinal bleeding requiring an overnight hospitalization for monitoring purposes would be considered an SAE, but is not necessarily severe. Similarly, an AE that is severe in intensity is not necessarily an SAE. For example, alopecia may be assessed as severe in intensity, but would probably not be considered an SAE.

A blood sample for MN-001 concentration will be obtained when a subject experiences a SAE.

## **12.5.1.** SAE Reporting Requirements

The PI or an authorized delegate is responsible for faxing the requested information to the Sponsor or designee within 24 hours or as soon as possible after learning of the event. Following the end of the subject's participation in the study, the PI or an authorized delegate should report SAEs "spontaneously" if considered at least possibly related to study medication.

Notification should be made by emailing a completed SAE Report Form to the Sponsor. Study sites in the US should email a completed SAE Report Form to:

[contact].As a minimum requirement, the initial notification should provide the following information:

- Study number
- Subject number
- Gender
- Date of birth
- PI's name and full study site address
- Details of SAE
- Criterion/criteria for classification as "serious"
- Study medication name, or code if blinded, and treatment start date
- Date of SAE onset
- Causality assessment (if sufficient information is available to make this classification).

Initial reports of SAEs must be followed later with detailed descriptions, including clear photocopies of other documents as necessary (e.g., hospital reports, consultant reports, autopsy reports, etc.), with the study subject's personal identifiers removed. All relevant information obtained by the PI or an authorized delegate through review of these documents will be recorded on the AE eCRF page and/or a new SAE Report Form and faxed to the Sponsor or designee within 24 hours of receipt of the information. If a new SAE Report Form is faxed, the PI must sign and date the form. The Sponsor may also request additional information on the SAE, which the PI or an authorized delegate must fax to the Sponsor or designee within 24 hours of the request using a new SAE Report Form, bearing the PI's signature and date.

Any AE fulfilling the criteria for expedited reporting will be reported by the Sponsor to regulatory authorities and Investigators and IEC(s) in accordance with the Sponsor's standard operating procedures (SOPs) and local regulatory requirements.

PIs should report all Investigational New Drug Application safety alerts received from the Sponsor to their local IRB/IECs.

#### 12.6. Guidance for Overdose

There is no clinical experience with MN-001 overdose in humans and there is no available specific antidote to the effects of MN-001. Standard symptomatic support measures should be used in the case of excessive pharmacological effects or overdose.

## 12.7. Reporting and Follow-up of Pregnancies

If any study subject or subject's partner becomes pregnant after receiving the first dose of study medication (MN-001) and until the follow-up period specified in the protocol, the PI or an authorized delegate should submit a Pregnancy Report Form to the sponsor within 24 hours of the PI or an authorized delegate first becoming aware of the pregnancy. If a pregnancy is to be terminated, the anticipated date of termination should also be provided in the "Additional Information/Comments" field of the Pregnancy Report Form. If a maternal SAE is reported for the study subject during the initial notification of pregnancy, a separate SAE Report Form should also be completed and submitted to the sponsor within 24 hours of the PI or an authorized delegate first becoming aware of the SAE.

Subjects who become pregnant while in the study should be followed for the duration of their pregnancy. If the pregnancy is discovered between regularly scheduled study visits, subjects should return for an unscheduled visit to return their study medication. A quantitative  $\beta$ -hCG should be obtained and subjects should be encouraged to return for follow-up visits. If follow-up visits are not possible, then the principal investigator should collect information about the pregnancy such as spontaneous or elective termination, details of birth, and presence or absence of birth defects, congenital abnormalities, or maternal and newborn complications.

The Sponsor will request that the PI follow the progress of the study subject's pregnancy with the doctor medically responsible for the pregnancy. A new Pregnancy Report Form should be submitted within 24 hours of the PI or an authorized delegate first becoming aware of any new information.

If additional information on the outcome of the pregnancy and/or the details of the birth/delivery is received "spontaneously" by the study site, the PI or authorized delegate should also submit a Pregnancy Report Form within 24 hours of becoming aware of the information. If the outcome of the pregnancy is reported as premature birth, or as elective termination due to a medical reason or as spontaneous or accidental miscarriage, the details of the outcome should be described in the "Additional Information/Comments" field of the Pregnancy Report Form. The pregnancy outcome will generally be reported as a follow-up report.

Complete an SAE Report Form if the delivery outcome meets the criteria for a SAE (e.g., congenital anomaly/birth defect, stillbirth, some other sickness, etc.). The SAE Report Form should be completed with the study subject's details (e.g., subject number, initials, date of birth, investigational product information, etc.) and the details of the fetal SAE and maternal complications should be described in the "Narrative" field of the SAE Report Form.

If a pregnancy is reported for the study subject's partner, the sponsor will provide instructions on how to collect pregnancy information in accordance with local requirements.

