### Follow-up Visit (Week 13)

All subjects who complete the study will return for a follow-up visit at Week 13. At the last visit a physical examination including body weight, vital signs, and safety labs will be done. Adverse events and concomitant medications will be collected.

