### STUDY ENTRY CRITERIA:

#### Inclusion Criteria:

- Written informed consent is obtained and willing and able to comply with the protocol in the opinion of the Investigator.
- Male or female subjects age  $\geq 18$  years of age
- Histologically proven NASH (NAFLD activity score of 3 or greater with at least 1 point being ballooning) based on liver biopsy performed within the last 36 months or NAFLD confirmed by imaging studies.
- Fasting serum triglyceride level > 150 mg/dL (confirmed at screening)
- Serum ALT, AST, ALP and total bilirubin levels at Screening (- 120 days to 30 days) and Lab Visit values (- 1 week ± 5 days) are stable or changes at the Lab visit are < 20% of the values from Screening.
- Subjects on the following medications can be enrolled if these medications are necessary, cannot be stopped, and the dose has been stable for 3 months or more prior to baseline:
  - o Stable doses of anti-diabetic medications
  - o Stable doses of fibrates, statins, niacin, ezetimibe
  - o Stable doses of Vitamin E for at least 8 weeks
- Less than 21 units of alcohol/week for men and 14 units of alcohol/week for women over a 2year time frame
- Females of child-bearing potential must have a negative serum β-hCG at screening and must be willing to use appropriate contraception (as defined by the investigator) for the duration of study treatment and 30 days after the last dose of study treatment
- Males should practice contraception as follows: condom use and contraception by female

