# 6. OVERALL STUDY DESIGN AND PLAN: DESCRIPTION

The study will consist a Screening Phase (up to 4 months) followed by a Treatment Phase (12 weeks), and a Follow-up visit (within 1 week after the last dose).

A total of 40 male and female subjects  $\geq 18$  years of age are planned to be enrolled.

The study phases are described below and displayed in Figure 1 and the Schedule of Assessments is displayed in Table 1.

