# 7.2. Inclusion/Exclusion Criteria

### 7.2.1. Inclusion Criteria

- Written informed consent is obtained and willing and able to comply with the protocol in the opinion of the Investigator.
- Male or female subjects  $\geq 18$  years of age
- Histologically proven NASH (NAFLD activity score of 3 or greater with at least 1 point being ballooning) based on liver biopsy performed within the last 36 months or NAFLD confirmed by imaging studies.
- Fasting serum triglyceride level > 150 mg/dL (confirmed at screening)
- Serum ALT, AST, ALP and total bilirubin levels at Screening (- 120 days to -30 days) and Lab Visit values (- 1 week ± 5 days) are stable or changes at the Lab visit are < 20% of the values from Screening.
- Subjects on the following medications can be enrolled if these medications are necessary, cannot be stopped, and the dose has been stable for 4 months or more prior to baseline:
  - Stable doses of anti-diabetic medications
  - Stable doses of fibrates, statins, niacin, ezetimibe.
  - Stable doses of Vitamin E for at least 8 weeks
- Less than 21 units of alcohol/week for men and 14 units of alcohol/week for women over a 2-year time frame
- Females of child-bearing potential must have a negative serum ß-hCG at screening and must be willing to use appropriate contraception (as defined by the investigator) for the duration of study treatment and 30 days after the last dose of study treatment.
- Males should practice contraception as follows: condom use and contraception by female partner.
- Subject is in good physical health on the basis of medical history, physical examination, and laboratory screening, as defined by the investigator.
- Subject is willing and able to comply with the protocol assessments and visits, in the opinion of the study nurse/coordinator and the Investigator.

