#### 8.8.1.3. Follow Up Phase

#### Visit 8: Week $13 \pm 3$ days

- Body weight/waist circumference
- Vital signs
- Physical examination
- Adverse event review

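### Section 12.7 stops requiring pregnancy reports at a follow-up about one week after the last dose, while female contraception is required for 30 days, so about 23 of those days have no reporting trigger

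*Combined protocol and SAP*

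**What the plan says.** **Reporting.** Protocol Section 12.7 asks for a Pregnancy Report Form if a subject or a subject's partner "becomes pregnant after receiving the first dose of study medication (MN-001) and until the follow-up period specified in the protocol". The form is due within 24 hours of the site learning of the pregnancy. The section does not say how long the follow-up period is.

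**Follow-up.** Section 6 provides for "a Follow-up visit (within 1 week after the last dose"). The synopsis adds: "All subjects who complete the study will return for a follow-up visit at Week 13". Section 6.1.3 likewise ties this visit to completers. Table 1 allows 5 days either side of Week 13; Section 8.8.1.3 allows 3.

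**Contraception.** Women able to conceive must use contraception "for the duration of study treatment and 30 days after the last dose of study treatment" (Section 7.2.1; the synopsis agrees). For men, Section 7.2.1 says only: "Males should practice contraception as follows: condom use and contraception by female partner". No end date is given.

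**Testing.** Table 1 of the protocol and Table 1 of the SAP show pregnancy tests at screening, the lab visit, and Weeks 4, 8 and 12/early termination. The Week 13 cell is blank in both, and the Visit 8 list in Section 8.8.1.3 has no test.

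**The concern.** The protocol sets a period after the last dose in which it wants pregnancy avoided, but asks sites to report pregnancies over a much shorter one. A site applying 12.7 exactly would send no form for a conception on, say, day 15 after the last dose, although a female subject is still under the contraception requirement that day. A pregnancy that is never reported is not followed to outcome, and that follow-up is what 12.7 provides.

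Two further gaps lie alongside this. Subjects who stop early have an early termination visit with a urine test, but Week 13 is promised only to completers, so the end of their reporting window is undefined. Partner pregnancies are reportable, but the male clause has no duration against which a reporting window could be set.

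**Working it through.** The plan gives no figure to reproduce, because 12.7 states no number of days. The check is day arithmetic.

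**Inputs**
- Contraception after the last dose: 30 days (Section 7.2.1, synopsis).
- Nominal follow-up: Week 13 − Week 12 = 1 week = 7 days, which agrees with the one-week rule in Section 6.
- Visit windows: ± 5 days (Table 1) and ± 3 days (Section 8.8.1.3).
- Last dose taken to fall at nominal Week 12, except in the last row below.

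**Formula:** days without a reporting trigger = 30 − days from last dose to follow-up; share = that number / 30.

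| Reading of the follow-up | Day after last dose | Days without trigger | Share |
|---|---|---|---|
| Nominal Week 13 | 7 | 30 − 7 = 23 | 76.7% |
| Within one week | 0 to 7 | 30 to 23 | 100% to 76.7% |
| Week 13 ± 3 days | 4 to 10 | 26 to 20 | 86.7% to 66.7% |
| Week 13 ± 5 days | 2 to 12 | 28 to 18 | 93.3% to 60.0% |
| Week 12 five days early, Week 13 five days late | 7 + 5 + 5 = 17 | 13 | 43.3% |

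Follow-up on day 10, 12 or 17 breaks the one-week rule, so 20, 18 and 13 days are sensitivity figures. Every reading that respects the rule leaves 23 to 30 days. If the phrase in 12.7 means the start of follow-up, taken as the end of treatment, all 30 days are uncovered.

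**Testing.** The last scheduled test is at Week 12/early termination, so all 30 days pass without one. The synopsis says of the final visit: "At the last visit a physical examination including body weight, vital signs, and safety labs will be done". Appendix 1 lists beta-hCG among the laboratory tests, which might suggest that the Week 13 labs include it. Table 1 does not support that: the pregnancy test has its own row, blank at Week 13, and the earlier visit lists name beta-hCG separately from the safety labs.

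**What triggers a report.** Section 12.7 turns on when the pregnancy begins; the 24-hour clock starts when the site learns of it. There are therefore two cases:
- Conceived between first dose and follow-up, recognised later: inside the window, so reportable as written.
- Conceived after follow-up and up to day 30 (days 8 to 30 at the nominal visit): no trigger, whenever recognised.

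**The case against.** The strongest reply is that a contraception margin longer than the reporting window is a choice, not a contradiction. The 30 days appear in an inclusion criterion. The documents do not call them an exposure or surveillance window, and nothing in them shows residual drug on day 15. That stands, and a reader should not infer that the protocol itself declares a 30-day risk period. The narrower point remains: the only post-dose pregnancy period the protocol sets is 30 days, and the reporting rule uses a different, undefined one.

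A reader might also infer that pregnancies conceived on drug in the last dosing weeks escape reporting if they surface after Week 13. The documents do not support this, since 12.7 sets no cut-off on discovery. What can be said is that no scheduled check would find them and that 12.7 leaves the rule implicit.

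Other safeguards exist but are partial. Week 13 includes a physical examination and adverse event review. After participation ends, Sections 12.3 and 12.5.1 keep open spontaneous reporting of serious events thought at least possibly drug-related, and a congenital anomaly counts as serious. An uncomplicated pregnancy does not, so it would prompt no report by that route. The consent form was not available for review. It may ask subjects to report later pregnancies, but that would not change what 12.7 tells sites to do.

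**Conclusion.** The mismatch holds. At the nominal Week 13 visit, 23 of the 30 post-dose contraception days (77%) have no reporting trigger, and 23 to 30 days under the one-week rule. This rests on reading the Week 13 visit as the follow-up period, the only one the protocol specifies, and on the last dose falling at Week 12. The 30-day comparison applies to female subjects only.

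The percentages describe calendar days, not expected missed pregnancies: the documents do not say how many of the 40 planned subjects could become pregnant or have partners who could. No endpoint or efficacy analysis is affected. This is an inexpensive improvement to safety capture that changes what sites report.

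**What to change.** - In Section 12.7, replace the reference to the follow-up period with an explicit end at the protocol's existing 30 days after the last dose, and say that it also applies to subjects who terminate early.
- Add that a pregnancy with estimated conception inside that window is reportable whenever it is discovered. This makes explicit what the wording already implies for on-drug conceptions and extends it to day 30.
- Add one telephone question at day 30 for the subjects concerned. It finds only pregnancies known by then; the preceding sentence covers later recognition.
- The sponsor should reconcile the male contraception clause with the partner-reporting window so that both state the same period. No contraception duration and no added test is proposed here.

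The cost is a wording amendment and one short call to a subset of subjects. Treatment, enrolment and existing visits are unchanged.
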